
### AIM:

To determine if short-term use of continuous glucose monitoring systems (CGMS) with intensive real time feedback about diabetes management from medical staff to the patient will affect motivation and/or behavior, in adolescents with poorly controlled type 1

CONFIDENTIAL

This material is the property of the NYU School of Medicine and Langone Medical Center. Do not disclose or use except as authorized in writing by the study sponsor

Use of continuous glucose monitoring system with intensive feedback in adolescents with poorly controlled type 1 diabetes  
Version Date: 04/26/2018

diabetes. Previous CGMS studies have tended to focus on participants who are in better glycemic control at baseline and who report better adherence and diabetes-related quality of life than expected of a randomly selected sample of subjects with type 1 diabetes.

Studying a more broadly representative group that includes subjects with poor glycemic control will provide helpful information about glycemic and psychological effects of CGMS in an at risk group(1). Research indicates that various psychological skills and psychosocial factors, including coping and social support play a large role in the efficacy of CGMS use(2).

We hypothesize that short-term CGMS use with feedback (and/or lack thereof) and patients' sense of self-efficacy will influence their stage of change and potentially glucose levels.

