#### SUBJECTS:

Sixty adolescents, ages 13-22 years, with type 1 diabetes and an HbA1c  $\geq 8\%$  who are also naive to CGMS or who have not used a CGMS in at least six months use will be recruited from the diabetes outpatient population followed at Bellevue Hospital, Lutheran Hospital, Woodhull Hospital, and the NYU Fink Pediatric Ambulatory Care Center. Forty subjects will be randomly assigned to the CGMS group and 20 subjects will be assigned to the control group.

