#### CONFIDENTIAL

This material is the property of the NYU School of Medicine and Langone Medical Center. Do not disclose or use except as authorized in writing by the study sponsor

Use of continuous glucose monitoring system with intensive feedback in adolescents with poorly controlled type 1 diabetes  
Version Date: 04/26/2018

appointments and staff will determine if they are interested in participation in the study using a recruitment script uploaded under recruitment materials section.

The study is minimal risk (MR). The device is approved by the FDA and is being used according to its cleared/approved labeling. The probability and magnitude of harm or discomfort anticipated in this research is similar to those ordinarily encountered in daily life or during the performance of routine physical or psychological examinations or tests.

The use of the CGMS will be described.

The study will consist of 4 phases.

1: For all participants at entry into the study the participant's HbA1c will be measured in the lab at the location of the patient's visit and his/her glucose meter will be downloaded as part of routine care. The average capillary glucose level, (with range and standard deviation) and the average number of tests per day over the prior 14 days will be recorded. The current individual care plans for self-management of type 1 diabetes will be reviewed by the study personnel with the participant.

Questionnaires will be administered to all the participants except Appendix F:

- 1) Appendix A - Stages of Change measure (original). We created a 5 item questionnaire to assess the patient's current stage.
- 2) Appendix B - Psychosocial self-efficacy (University of Michigan Diabetes Research and Training Diabetes Empowerment Scale short-form) - DES. 8 items. Also available for use.(3-6)
- 3) Appendix C - Knowledge and risk perception (University of Michigan Diabetes Research Training Center Diabetes Knowledge Scale). 23 items - DKT. We are substituting rapid acting insulin for NPH insulin in item 17 since NPH is not used in our study population. Available for use without permission as long as the source is quoted.(7, 8)
- 4) Appendix D - Quality of life (Peds QL 3.2, Diabetes module,) – Peds QL. 33 items on a Likert scale.(9)

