- 5) Appendix E - Depression (PHQ-2.). 2 items. If the patient receives a score of 3 or above, a referral to psychiatric services will be made. No permission required to reproduce, translate, display or distribute.(10, 11)
- 6) Appendix F – CGM Satisfaction Scale. To be administered at second visit. See below number 2 on protocol. Will only be administered to study group.
- 7) Appendix G - Demographic variables will be collected.
- 8) Appendix H - Telephone administered questionnaire.
9. Appendix I – data to be tabulated in research database in RedCap

---

[figure not shown]
CONFIDENTIAL

This material is the property of the NYU School of Medicine and Langone Medical Center. Do not disclose or use except as authorized in writing by the study sponsor

Use of continuous glucose monitoring system with intensive feedback in adolescents with poorly controlled type 1 diabetes  
 Version Date: 04/26/2018

Standard scoring will be used for the DKT, DES, PHQ-2 and Peds QL.  
 Standard scoring instructions will be followed for published tests.  
 The CGMS will be used only in the study group. The CGMS that will be used will be Dex-COM® which consists of the sensor, transmitter and the receiver. The Dex-COM CGM device is FDA approved for use in patients 2 years and older.

**Sensor** - The sensor is packaged in a sterile sealed pouch, containing an applicator, sensor pod and sensor wire. The applicator barrel helps to insert the sensor wire inside the sensor pod under the skin. After inserting the sensor wire, the applicator barrel is removed. The sensor wire stays in the sensor pod with the pod attached to the skin by adhesive. The sensor wire is made of silver and platinum with polymer membranes. Once inserted, the thin and flexible wire measures the glucose levels in the fluid between the cells (interstitial fluid) for up to seven days. Dexcom sensor is inserted in the belly/abdomen (ages 2 years and older) or the upper buttocks (ages 2 to 17 years). The sensor is water resistant

**Transmitter** - Snapping into the sensor pod, the gray plastic transmitter wirelessly sends your glucose information to your display devices—receiver. The transmitter is re-usable and water-resistant.

CONFIDENTIAL

This material is the property of the NYU School of Medicine and Langone Medical Center. Do not disclose or use except as authorized in writing by the study sponsor

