3. Study visit #3 will be scheduled at 1 month for both the study and control groups. The patient's glucose meter will be downloaded and the data will be extracted as above. The Empowerment Scale short-form, Quality of Life, Family Management Measure and the Stages of Change questionnaires will be administered. There will be an open-ended interview with the participant. The patient will be given \$20 on completion at this visit.

4: Study visit #4 will be scheduled at 3 months for both the study and control groups. The patient's HbA1c will be measured in the lab at the location of the patient's visit, his/her glucose meter will be downloaded and the data will be extracted as above. The Empowerment Scale short-form, PHQ-2, Quality of Life and the Stages of Change questionnaires will be administered. The patient will be given \$20 on completion at this visit.

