#### ANALYSIS:

Measures of the level of glycemic control will be assessed primarily by HbA1c and secondarily by the average glucose tests results on the patient's glucose meter. Comparison of the glucose results (average, range, standard deviation, number of daily tests) between the study entry, 1 week, 1 month and 3 month follow up visits will be done. Comparison of HbA1c at entry and at 3-month follow-up will be performed. Questionnaire scores will be compared between study entry, 1 week follow up, 1 month follow up and 3-month follow-up visits for DES and Stages of Change scales. We will determine if there is a correlation between the scores on the questionnaires and measures of glucose control. We will classify study and control participants into adherent and non-adherent groups.

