Demographics (Appendix G): data will be put in table form, with range, mean, s.d. scores for age; % Male/Female; and descriptive data for the remainder of the items. In Questions #11, 13 and 14, with 1-5 scales, the range, mean, and s.d. scores will be given. Stages of Change (Appendix A): scores can be given categorically, with each question assigned a score of 1 for a “yes” answer, and zero for a “no” answer; then range, mean, s.d. will be calculated before and after the intervention. In addition, a “yes” or “no” answer to these questions will determine which “stage of change” category the subject belongs in, according to the definition of “stages of change”. This is categorical data. We will analyze movement in the “stages of change” by comparing the score before and after the study intervention. This will be categorical: improvement, no change, deterioration.

CONFIDENTIAL

This material is the property of the NYU School of Medicine and Langone Medical Center. Do not disclose or use except as authorized in writing by the study sponsor

Use of continuous glucose monitoring system with intensive feedback in adolescents with poorly controlled type 1 diabetes  
Version Date: 04/26/2018

Diabetes Empowerment Scale-Short Form (Appendix B): the average of the scores of the completed items will be tabulated. Each question is answered as 1-5, and there are 8 questions. Thus, the scores can range from 1-5. The scores will be compared before and after study intervention.

Diabetes Knowledge Test (Appendix C): There are 23 multiple choice questions, scored as correct or incorrect. This will be administered only at baseline.

Peds Quality of Life 3.2 Diabetes Module: (Appendix D): There are 33 questions with Likert scale answers (0-4). Scores are transformed on a scale of 0-100. This test will be administered before and after the study intervention.

PHQ-2: (Appendix E): The score ranges from 0-6. The scores will be compared before and after the study intervention.

CGM Satisfaction Scale: (Appendix F): We are using an abbreviated version of a previously published CGM-SAT scale. Each question is scored 1-5 and the mean is calculated. This will be given after the intervention and only in the intervention group.

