Daily Phone Log: (Appendix H): Scoring will be done for each day of the initial week of the study, in both CGM intervention group, and control group based on the following: Study subjects will receive points for calibrating the CGM device and for successfully completing phone contact with the pediatric diabetes team. The patient will receive 2 points for calibrating the device 2 times/day for at least 5 days, 1 point for calibrating the device 2 times on at least 3 days and 0 points for calibrating any less. Similarly the patient will receive 2 points for completing successful phone contact with study personnel for at least 5 days, 1 point for completing phone contact on at least 3 days and 0 point for contact any less than mentioned before. The two scores will be added to get a total score. Patients with scores 3-4 will be classified as adherent and scores 0-2 will be classified as non-adherent. Control subjects who complete 4 or more phone calls on different days will be classified as adherent and those who complete fewer phone calls will be classified as non-adherent.

The distribution of the data will be assessed using the Kolmogorov-Smirnov test. All categorical variables will be presented as mean +standard deviation. For categorical variables the differences between the compliant and non-compliant groups will be assessed using the Mann Whitney or rank order Wilcoxon test based on normality. For categorical variables independent sample t test will be used. Univariate analysis will be used to establish correlation between variables of interest.

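### PHQ-2 is planned only as a before-after comparison, although both randomised arms complete it and high scorers are referred, so a change cannot be attributed to CGMS

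*Combined protocol and SAP*

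**What the plan says.** All references are to the combined protocol and SAP.

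- **Purpose.** The AIM section says that studying poorly controlled patients "will provide helpful information about glycemic and psychological effects of CGMS in an at risk group".
- **Design.** SUBJECTS: "Forty subjects will be randomly assigned to the CGMS group and 20 subjects will be assigned to the control group".
- **Entry measurement.** METHODS, phase 1: "Questionnaires will be administered to all the participants except Appendix F". Appendix F is the CGM satisfaction scale, so the PHQ-2 (Appendix E) goes to both arms.
- **Referral rule.** In the same list, under Appendix E: "If the patient receives a score of 3 or above, a referral to psychiatric services will be made". The rule is not limited to one arm.
- **Follow-up measurement.** Study visit #4, at 3 months and for both groups: "The Empowerment Scale short-form, PHQ-2, Quality of Life and the Stages of Change questionnaires will be administered".
- **Analysis.** ANALYSIS, Statistical Analysis for sensor study, PHQ-2: "The score ranges from 0-6. The scores will be compared before and after the study intervention". The text names no test and does not say whether the comparison is pooled over arms or made within the CGMS arm.
- **Groups named for testing.** The closing paragraph of the analysis section says "differences between the compliant and non-compliant groups will be assessed using the Mann Whitney or rank order Wilcoxon test based on normality". These are adherence groups, not the randomised arms.

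**The concern.** The trial has a randomised control arm that follows the same PHQ-2 schedule under the same referral rule, and the written PHQ-2 analysis does not use it as a comparator. Three months pass between the two scores. For anyone at 3 or above, the entry score itself prompts psychiatric referral in that interval. A fall in PHQ-2 could come from the device and feedback, from referral, or from time, and a before-after comparison cannot separate them.

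What is at stake is attribution: the AIM section promises information on psychological effects of CGMS, and a significant fall in PHQ-2 could be read as one. Individual care is not at issue, and the referral rule is right.

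The missing arm contrast is not confined to PHQ-2. HbA1c, for instance, is covered by "Comparison of HbA1c at entry and at 3-month follow-up will be performed". The referral triggered by the score is specific to PHQ-2.

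**Working it through.** **Is an arm contrast stated anywhere?** Four other sentences in the analysis section could bear on PHQ-2:

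- the correlation of questionnaire scores with glucose control, which is not an arm comparison;
- the paired t-test, named only for stages of change;
- the rank test, which is for compliant versus non-compliant groups;
- an independent-sample t test and a univariate analysis, for which no groups are named.

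None of these states CGMS versus control.

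**How large could the misattribution be?** The plan gives no alpha, SD, prevalence, referral uptake or effect size, so there is no figure of its own to reproduce. Everything below is assumed except the 40:20 split and the 0-6 scale.

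- Share scoring 3 or more at entry: 15%, 25% or 35%. The assumed probabilities for scores 0 to 6 are .40/.20/.25/.07/.04/.02/.02, .32/.18/.25/.11/.07/.04/.03 and .25/.15/.25/.15/.10/.06/.04. Expected referrals at entry are 0.15 × 40 = 6 to 0.35 × 40 = 14 in the CGMS arm, and 3 to 7 of 20 in the control arm.
- Entry and 3-month scores are linked by a normal copula with latent correlation 0.5. Referral and trend act as shifts on the latent SD scale.
- CGMS effect: none. Two-sided 5% level, no dropout, 10,000 trials per scenario. A paired t-test is used because the plan names no test.

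Percentage of trials with a significant before-after change in the 40 CGMS subjects:

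| Scenario | 15% positive | 25% positive | 35% positive |
|---|---|---|---|
| No referral effect, no trend | 4.5 | 5.0 | 5.0 |
| Referral 0.5 SD, 50% uptake | 5.3 | 6.3 | 8.2 |
| Referral 0.5 SD, 100% uptake | 7.4 | 10.5 | 16.5 |
| Referral 1.0 SD, 50% uptake | 6.6 | 9.6 | 14.0 |
| Referral 1.0 SD, 100% uptake | 11.7 | 21.9 | 38.8 |
| Trend -0.1 SD only | 8.5 | 8.5 | 9.3 |
| Trend -0.2 SD only | 18.0 | 19.0 | 20.6 |
| Trend -0.3 SD only | 34.4 | 36.6 | 38.1 |

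Pooling all 60 makes it worse: the first five rows at 25% positive become 5.2, 7.2, 14.1, 12.6 and 31.3. The mean change produced by referral alone runs from 0 to -0.59 points.

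**Hand check of the trend effect.** On a continuous scale the SE of the mean change is √(2(1-ρ)/n) = √(2 × 0.5/40) = 0.158 SD. A shift of 0.2 SD gives 0.2/0.158 = 1.26, and Φ(1.26 - 1.96) ≈ 0.24. This is the same order as the 18-21% in the table; the coarse 0-6 scale lowers it somewhat.

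**The arm comparison, same data.** Regress the 3-month score on arm and entry score.

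- Equal uptake and trend in both arms: 4.7-5.5% significant.
- Uptake 80% in the CGMS arm and 30% in control, referral 0.5 SD: 4.9, 5.8 and 6.4% at 15, 25 and 35% positive (mean estimates -0.06, -0.11, -0.15 points).
- The same uptake with 1.0 SD: 5.7, 8.3 and 10.5% (mean estimates -0.10, -0.20, -0.28 points).

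**Precision of the arm comparison.** The median 95% half-width is 0.60-0.85 points across scenarios. A hand check at 25% positive, where the assumed distribution has SD 1.61, gives 2.00 × 1.61 × √(1 - 0.5²) × √(1/20 + 1/40) = 0.76. The difference detectable with 80% power is the half-width × (2.00 + 0.85)/2.00, that is 0.86 to 1.21 points.

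**The case against.** The strongest reply is about weight. PHQ-2 is a two-item screen that carries a clinical referral rule. It is not among the listed dependent variables, and the main hypothesis concerns stage of change and glucose. Nothing in the plan says a PHQ-2 change will be credited to the device, and a descriptive before-after summary is not wrong in itself. The larger defect is the absence of an arm contrast for every outcome, and PHQ-2 is only one instance of it. The part unique to PHQ-2, the referral, adds little in the central case (6% to 10.5% against 5%). The 39% needs a high prevalence, a large effect and full uptake together, and an assumed time trend can do as much.

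The rates also depend on modelling choices. Subtracting the same effects from the 0-6 score with a floor at zero gives 5.7% and 9.0% in the central case, 32% in the corner case and about 7-29% for trend alone. Finally, the corrected analysis has an interval wider than any referral-driven change simulated.

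All of this stands as an argument about severity, and it is why the point is minor. It does not supply the missing contrast. Randomisation does not imply one when the plan spells out other contrasts and leaves this one out. The weak precision of the arm comparison is also no reason to rely on a before-after test that answers a different question.

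**Conclusion.** The concern holds, as a minor point. It is certain from the text that the only comparison written for PHQ-2 itself is before versus after, that both arms supply both scores, and that scores of 3 or more lead to referral. That analysis cannot isolate a CGMS effect.

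The size is unknown. It depends on prevalence, referral uptake and effect, and trend, none of which the documents give, and it may be zero. Under the assumptions above, the false-positive rate in the CGMS arm goes from 5% to about 6-10.5% in the central case, with 39% as an upper corner, and a modest shared trend can matter as much as referral.

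The arm comparison removes whatever the two arms share. It does not remove a difference in referral uptake, which arises after allocation and belongs to the effect of assignment.

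**What to change.** Leave the referral rule as it is. In the PHQ-2 entry of the analysis section, replace the before-after sentence with:

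> The visit-4 PHQ-2 score will be compared between the assigned CGMS and control groups, adjusted for the entry score, with a 95% confidence interval. No within-group change will be attributed to the device. Referrals made and known referral uptake will be reported by group. Any difference in uptake is part of the effect of assignment.

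A table by arm of status at the cut-off of 3 is optional and descriptive. Because the score is short and skewed, a rank-based or ordinal model is a reasonable alternative to the linear one. The other outcomes in the analysis section, HbA1c first, need the same kind of arm contrast.

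The cost is wording, plus a count of referrals and known uptake by arm. Uptake is not among the data described for the visits, so that item is a small new collection; no visit or questionnaire is added. The price in precision is real: with 40 versus 20 the interval is about ±0.6 to 0.9 points, so only differences of roughly 0.9 to 1.2 points would be detected with 80% power. The change guards against misattribution and is unlikely to demonstrate a PHQ-2 effect, so the comparison is best labelled exploratory.

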#### CONFIDENTIAL

This material is the property of the NYU School of Medicine and Langone Medical Center. Do not disclose or use except as authorized in writing by the study sponsor

Use of continuous glucose monitoring system with intensive feedback in adolescents with poorly controlled type 1 diabetes  
Version Date: 04/26/2018

Dichotomizing participants into adherent and non-adherent:

Study subjects will receive points for calibrating the CGM device and for successfully completing phone contact with the pediatric diabetes team. The patient will receive 2 points for calibrating the device 2 times/day for at least 5 days, 1 point for calibrating the device 2 times on at least 3 days and 0 points for calibrating any less. Similarly the patient will receive 2 points for completing successful phone contact with study personnel for at least 5 days, 1 point for completing phone contact on at least 3 days and 0 point for contact any less than mentioned before. The two scores will be added to get a total score. Patients with scores 3-4 will be classified as adherent and scores 0-2 will be classified as non-adherent. Control subjects who complete 4 or more phone calls on different days will be classified as adherent and those who complete fewer phone calls will be classified as non-adherent.

Statistical methods:

Demographic data will be tabulated. Statistical analysis of questionnaires will be done according to published standards. The paired t-test will be used for comparisons involving stages of change score.

Independent variables will include the empowerment score, average glucoses, HbA1c and whether the subjects fall into the adherent vs. non-adherent groups. Dependent variables include glucose level(s) and stage of change. We will analyze the 7 day average glucose by meter download and categorize the results in terms of change: No change (-15 to + 15), Higher ( $\geq + 15$ ) or Lower ( $\leq -15$ ). We will analyze the HbA1c and categorize the results in terms of change: No change ( $> -0.5$  to  $+ 0.5$ ), Higher ( $\geq + 0.5$ ) or Lower ( $\leq -0.5$ ). Stages of change (Appendix A) will be categorized as unchanged, improved or worsened. In addition, descriptive statistics including quality of life, diabetes knowledge scale, and demographic variables will be tabulated.

Statistical Analysis for sensor study:

Questionnaires:

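### Adherence is defined by a different rule in each arm, but the adherent versus non-adherent comparison has no arm term or stratum; if the arms are pooled it can carry part of any arm effect

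*Combined protocol and SAP*

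**What the plan says.** The adherence rules stand under the ANALYSIS heading, in the paragraph on dichotomising participants, and are repeated under Daily Phone Log (Appendix H).

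- **CGMS arm.** Calibration earns 2 points for twice-daily calibration on at least 5 days, 1 point for at least 3 days, and otherwise 0. Phone contact is scored the same way. On the total, "Patients with scores 3-4 will be classified as adherent and scores 0-2 will be classified as non-adherent".
- **Control arm.** There is no calibration part: "Control subjects who complete 4 or more phone calls on different days will be classified as adherent".
- **Window.** "Scoring will be done for each day of the initial week of the study, in both CGM intervention group, and control group".

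The rules differ for a practical reason stated under METHODS: "The CGMS will be used only in the study group".

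On use of the classification, ANALYSIS says "We will classify study and control participants into adherent and non-adherent groups". Statistical methods lists the independent variables as empowerment score, average glucoses, HbA1c and "whether the subjects fall into the adherent vs. non-adherent groups"; randomised arm is not listed. The dependent variables are glucose level and stage of change. The closing paragraph after the Daily Phone Log says "the differences between the compliant and non-compliant groups will be assessed using the Mann Whitney or rank order Wilcoxon test", depending on normality, and then "Univariate analysis will be used to establish correlation between variables of interest". I take compliant and adherent to mean the same thing. SUBJECTS gives 40 CGMS and 20 control subjects.

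**The concern.** Separate rules are reasonable, because controls have no device to calibrate. The difficulty comes when one label with two meanings is used as a single grouping variable. The same phone behaviour can then fall on opposite sides of the comparison according to arm. Each adherence group will generally hold a different mix of CGMS and control subjects, and a test without an arm term cannot separate the effect of adherence from the effect of arm.

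At stake is the interpretation of the adherence result. An arm effect on glucose or stage of change could be reported as a benefit, or a harm, of adherence. Compliant versus non-compliant is also the only between-group comparison in the plan whose groups are named alongside a test, so readers are likely to look at it.

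**Working it through.** The plan gives no figure to reproduce. It states no alpha, power, SD or completion rates. The rules and the 40:20 allocation come from the plan; every rate and effect size below is my assumption.

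**1. Same calls, opposite label.**
- 4 call days: a control is adherent. A CGMS subject with 4 calibration days scores 1 + 1 = 2 and is non-adherent.
- 3 call days: a control is non-adherent. A CGMS subject with 5 calibration days scores 1 + 2 = 3 and is adherent.

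**2. Adherence probabilities.** Let C be call days and K days with two calibrations. Each is binomial over 7 days, with daily rates p (equal in both arms) and q.
- Control: P(C ≥ 4).
- CGMS, tasks independent: P(K ≥ 5)·P(C ≥ 3) + P(3 ≤ K ≤ 4)·P(C ≥ 5).
- CGMS, both tasks done on the same days (C = K): P(C ≥ 5).

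**3. Arm mix.** Let a and c be the CGMS and control adherence probabilities. The adherent group has A = 40a + 20c expected members, and the non-adherent group N = 60 − A. The share difference is d = 40a/A − 40(1 − a)/N.

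Same-day case:

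| p | CGMS adherent | Control adherent | d (points) |
|---|---|---|---|
| 0.5 | 22.7% | 50.0% | −28.0 |
| 0.6 | 42.0% | 71.0% | −25.8 |
| 0.7 | 64.7% | 87.4% | −25.2 |
| 0.8 | 85.2% | 96.7% | −26.1 |
| 0.9 | 97.4% | 99.7% | −28.8 |

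At p = 0.6, A = 40(0.420) + 20(0.710) = 31.0. CGMS subjects are 54.2% of the adherent and 80.0% of the non-adherent.

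Independent case, calls 50–90% and calibration 40–90% in steps of 10 (30 combinations). In the 18 that expect at least 10 non-adherent subjects:
- d runs from −46.4 (p = 0.9, q = 0.4: 53.2% versus 99.7%) to +28.6 (p = 0.6, q = 0.9: 71.5% versus 42.9%).
- |d| is 10 points or more in 15 of the 18.
- At 60% for both tasks, a = 0.583, c = 0.710 and d = 62.1 − 74.2 = −12.1.
- It can vanish: d = +1.2 at p = 0.6, q = 0.7.

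The other 12 combinations leave too few non-adherent subjects for a useful comparison.

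**4. Bias and precision.** With no true adherence effect, the expected pooled difference is arm effect × d, and its standard error in SD units is √(1/A + 1/N). At an assumed arm effect of 0.5 SD:
- Same days, p = 0.6: 0.5 × (−0.258) = −0.13 SD; SE = √(1/31.0 + 1/29.0) = 0.26.
- Independent, p = q = 0.6: −0.06 SD; SE = √(1/37.5 + 1/22.5) = 0.27.
- Independent, p = 0.9, q = 0.4: −0.23 SD; SE = √(1/42.7 + 1/17.3) = 0.28.

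The largest ratio of bias to standard error among the 30 combinations is 0.83. This bound depends on the grid. At 30% calibration and 80% calling, d = −59.0 points, the bias is −0.295 SD, A = 31.5 and N = 28.5, so SE = 0.26 and the ratio is about 1.1.

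**5. False positives.** These come from 4,000 simulated trials per scenario, using a two-sided 5% t test with no adherence effect. At p = 0.6, same days, the pooled test rejects in 7.9% of trials for a 0.5 SD arm effect and 15.1% for 1.0 SD. At 60% for both, independent, the figures are 5.6% and 6.7%. With an arm term, rejection stays at about 4–6% throughout. With no arm effect, the pooled test also holds about 5%.

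**The case against.** **Pooling is not stated.** A reader might infer that the plan commits to pooling the arms. It does not. It says only that both arms are classified, and arm-specific rules would also suit a within-arm comparison. This stands, and the point is conditional on it. Still, one pair of groups, one two-sample test and no mention of arm make pooling the natural reading, and the choice would otherwise be left until the data are seen.

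**The text is loose.** The same paragraph mentions an independent-sample t test without naming groups; it could refer to study versus control. The univariate sentence does not name adherence either; the link runs through the list of independent variables. Both limits stand.

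**The arm effect may be small.** The bias needs one. The background says HbA1c did not improve in adolescents placed on CGM, and adherence is scored over a single week. This argues against large glycaemic effects; the 1.0 SD scenario in particular has no support in the documents. Stage of change could still differ by arm.

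**The −46 figure is an extreme.** It pairs 90% calling with 40% calibration and treats them as independent. Daily staff calls may well prompt calibration, so the same-day result of −25 to −29 points is the better guide.

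**Self-selection is probably the larger problem.** Adherence is not randomised, and an arm term does not change that. This stands too, and it is why the result should be described cautiously even after the fix.

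**Conclusion.** The point holds in conditional form, and its severity is minor. The rules differ by arm, both arms share one classification, and the stated analysis has no arm term or stratum. If the arms are pooled, part of any arm effect can pass into the adherence comparison. The direction is not fixed: the CGMS rule is stricter when calibration is poor or tracks calls, and looser when calibration is near complete.

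On assumed rates and an assumed 0.5 SD arm effect, the bias is about 0.13 SD in the same-day case, and below one standard error wherever calibration is 40% or better. It is zero if there is no arm effect.

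Two stronger conclusions might be drawn, and the documents support neither. Using two rules is not itself an error, since controls have nothing to calibrate. The randomised CGMS versus control comparison is not compromised, because it does not use the adherence label.

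**What to change.** Keep the arm-specific rules and add to the closing paragraph after the Daily Phone Log:

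*The adherent versus non-adherent comparison, and any correlation with adherence, will be adjusted for or stratified by randomised arm, and adherence will be tabulated by arm.*

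Show within-arm results descriptively, and only where numbers allow. Among the 20 controls, 60% calling would give about 14.2 adherent and 5.8 non-adherent subjects, with SE = √(1/14.2 + 1/5.8) = 0.49 SD. At 80% calling, only 0.67 non-adherent controls are expected, so the arm-adjusted estimate has to be the main one.

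The cost is one extra model term and a little precision; no new data are needed. With arm in the model, the standard error is 1/√[40a(1 − a) + 20c(1 − c)]. In the same-day case at 60% this is 1/√(9.74 + 4.12) = 0.27, against 0.26 unadjusted. At calls 90% and calibration 40% it is 1/√(9.82 + 0.05) = 0.32, against 0.28.
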